17.5 Qualitative assessments

No qualitative research will be performed as part of the study.

17.6 Withdrawal

Withdrawal of consent means that a participant (and/or their parent/guardian) has expressed a wish to withdraw from the study altogether or from certain aspects of the study only. The type of withdrawal will be collected on the CRF labelled 'Withdrawal'.

Participants may also be withdrawn from the study (or aspects of the study) by their clinician if they believe the participant needs to be withdrawn.

The Withdrawal CRF should be completed to document the reasons for withdrawal and state who the decision to withdraw was made by. Discussions and decisions regarding withdrawal should be documented in the participant's medical notes. Investigators should continue to follow up any SAEs and should continue to report any SAEs to resolution in the CRF in accordance with the safety reporting section.

Where a participant expresses a wish to withdraw from the study, the research team will determine which aspect(s) of the study the participant wishes to withdraw from.

The aspects of the study that the participant may request to withdraw from are as follows:

- No longer willing to have surgery
- No longer willing to complete study questionnaires
- No longer willing to attend study visits
- No longer willing to be contacted by the research team to obtain CRF/outcome data
- No longer willing to have routine data from the medical record provided to the study
- No longer willing for routine data from health data providers e.g. NHS England, to be provided to the study

Where a participant wishes to withdraw from all aspects of study participation detailed above this will be recorded on the Withdrawal CRF as full withdrawal.

In addition to participant self-withdrawal, an investigator may decide to withdraw a participant from study intervention for clinical reasons or other reasons such as non-compliance, eligibility. Participants and their parent/guardian will still be asked to participate in the collection of follow-up data. The reason for withdrawal will be recorded on the study withdrawal case report form.

Completion of the Withdrawal CRF by the site research team will trigger a notification to the central CTU study team. Appropriate action will be taken by the study teams (centrally at the CTU and by the site research team at each participating site) to ensure compliance with the participant's withdrawal request. This may include marking future CRFs as not applicable and ensuring any relevant communications which the participant had consented to receive regarding their participation are no longer sent.

Data collected up to the point of withdrawal will be used/analysed as explained in the PIS, unless the participant specifically requests otherwise.

18 BLINDING AND CODE BREAKING

18.1 Blinding

Table 2 provides an overview of the blinding status of all individuals involved in the conduct and management of the study.

Table 2: Blinding status of those involved in study conduct and management.

Role in study	Blinding status	Additional information
Participants	Blinded	All participants will be blinded to treatment allocation.
		In-theatre randomisation precludes any potential for patients to be unmasked or biased from cues prior to the operation. Patients will have a blinded operation note within their hospital medical records with the detailed operation case report form kept within the study paperwork.
Site research staff including Principal Investigator (may need to be broken down further if different levels of blinding/unblinding with the team)	Not blinded: Surgeons Blinded: aftercare personnel (physiotherapy), patient follow	It is not possible to blind the surgeons as to the procedure that they perform, but aftercare personnel (physiotherapy), patient follow up and research staff will be blinded to allocated intervention. Patient notes will refer to 'ACL surgery' not the treatment allocation. CRFs accessed by research staff will also not contain the treatment allocation.
with the team,	up and research staff	Following randomisation, an email will be sent to the PI (unblinded for participants they randomise only) and/or member of the site research team performing the randomisation (as delegated) confirming treatment allocation.
Chief Investigator	Blinded for those at sites other than their own, except for any SAE causality assessment	It is not possible to blind the Chief Investigator as they may be the primary clinician for those participants recruited at their site, however they will be blinded to allocations for participants at other sites. In instances where serious adverse events are reported, the CI will become unblinded to complete the full causality assessment.

Data collection system programmer	Not blinded	The programmer is responsible for the management of the randomisation system and the REDCap data collection system and will have access to all unblinded datasets within both systems.	
ACL STARR Central CTU Study Team	Not blinded	Will not be blinded to the allocation. Serious Adverse Event reports will be handled by the central CTU study team.	
Data Management	Not blinded	Data management staff will have access to the unblinded datasets within the study randomisation system and REDCap to ensure data quality and undertake central monitoring activities.	
Study Statistician and Senior Study Statistician	Not blinded	The study statistician and senior study statisticians will have access to treatment allocations or data needed for generating the Data and Safety Monitoring Committee (DSMC) closed reports and the final analysis.	
Health Economist	Not blinded	The study health economist will have access to treatment allocations or data needed for generating the final analysis.	

18.2 Code break/ unblinding

The operating clinician and the central study team will not be blinded to the allocation, so no code break procedure for clinical care or safety reporting is needed. The central study team will discuss specifically with each site which techniques they will employ to ensure participant and staff blinding. In any case in which unblinding is needed, or in which it occurs accidentally, the study team will follow processes as per the OCTRU Standard Operating Procedures (SOPs).

19 SAMPLES

This study protocol does not involve any taking of new biological samples or any use of pre-existing samples.

20 IMAGING

MRI is a standard of care investigation for patients with acute soft tissue knee injury. An MRI scan will be used as part of the assessment for initial eligibility assessment (see Section 11.3).

No images additional to standard care will be taken/collected as part of the study.

21 SAFETY REPORTING

21.1 Safety reporting period

For safety reporting the intervention is defined as ACL repair or reconstruction surgery (and post operative rehabilitation).

Safety reporting for each participant will begin from surgery and will end when the participant has reached their final main follow-up time point, at 24 months post-randomisation.

21.2 Definitions

Table 3: Definitions of Adverse Events

An adverse event (AE)	Any untoward occurrence in a clinical study participant. Note: An AE can therefore be any unfavourable and unintended sign (including an abnormal laboratory finding, for example), symptom or disease temporarily associated with the study procedures, whether considered related to the procedures. For ACL STARR, AEs will only be collected if relevant to the knee, the surgery, the anaesthesia or the rehabilitation and will be captured as complication data. It will be recorded on a complication CRF.		
Related Adverse Event	An event that resulted from administration of any of the research procedures		
Serious Adverse Event (SAE)	An AE that: • results in death • is life-threatening¹ • requires hospitalisation or prolongation of existing hospitalisation • results in persistent or significant disability or incapacity • is a congenital anomaly or birth defect; or • is otherwise considered medically significant by the Investigator²		
Unexpected Related Serious Adverse Event	A serious adverse event related to the study (i.e. resulted from administration of any of the research procedures) and is unexpected (not listed in the protocol as an expected occurrence).		

¹ participant was at risk of death at the time of the event; it does not refer to an event which hypothetically might have caused death if it were more severe

A distinction is drawn between serious and severe AEs. Severity is a measure of intensity whereas seriousness is defined using the criteria above. Hence, a severe AE need not necessarily be serious.

21.3 Expected adverse events

The expected adverse events related to the procedures are outlined below, and will be collected as complication data on CRFs, separating intra-operative complications, post-operative pre-discharge complications, and post-discharge complications. All complications will be graded using a standard classification, 'The Clavien-Dindo Classification of Surgical Complications' (38). Participants will be informed of the standard risks associated with the anaesthetic and the surgical procedure.

All ACL repair or reconstruction procedures whether primary surgery or revision carry a risk of
anaesthesia related problems which can include death, morbidity including wound infection,
bleeding intra and post operatively, pulmonary embolism (PE), deep vein thrombosis (DVT),
confirmed cerebrovascular accident (CVA), confirmed myocardial infarction (MI), and
complications secondary to existing comorbidity e.g. ischaemic heart disease, septicaemia, the
need for blood transfusion and revision operation.

² Medical events that may jeopardise the participant or may require an intervention to prevent one of the above characteristics/consequences.

- Specific complications following both ACL reconstruction and ACL repair procedures include:
 patella fracture, patella tendon avulsion, anterior knee pain, vascular injury and bleeding,
 femoral tunnel blowout, nerve damage (including numbness or weakness), complex regional
 pain syndrome, lack of extension/fixed flexion deformity, stiffness, infection, graft failure and
 continued instability, delayed wound healing, continued or worsened pain, fracture,
 compartment syndrome, swelling, additional contralateral graft harvest (reconstruction-only)
 and newly acquired meniscal pathology.
- Specific complications following rehabilitation include continued instability and subsequent newly acquired meniscal pathology causing pain. These complications may result in the need for further surgery.

21.4 Reportable AEs/SAEs

If participants experience any of the expected events listed in Section 21.3 and they also meet the definition of serious they would not be reportable to the REC. Only unexpected SAEs related to the study procedures are reportable to the REC.

As outlined above any expected adverse events related to the procedures will be collected as complication data on a CRF.

21.5 Procedure for collecting safety events from sites/participants

Details of all complications will be collected and recorded as detailed in Section 21.3. A final readmission checklist will be undertaken by the Research staff on hospital records at 24 months post randomisation to ensure that all complications data is collected from participants (i.e. those who had not returned a questionnaire). Data from readmission events identified will be recorded in the CRF.

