Time to return to sport To assess patient satisfaction with the outcome of treatment following ACL repair or reconstruction surgery	Patient satisfaction: 2 questions, Likert scale: 1. Would you have the treatment again if you could go back 2. Assessment of knee after versus before (is it better?)	12 and 24 months after randomisation 12 and 24 months after randomisation	 Return to Sport Questionnaire Patient Satisfaction Questionnaire 	Follow-up questionnaires. Completed by participants either on paper or entered directly into REDCap.	
To assess the complication co	Intervention related complications including re-operation	6, 12 and 24 months after randomisation Operative Postoperativel y up to 24 months after randomisation Review at the 24-month time point.	 Health Economics Questionnaire Case Report Form. 	Case Report Form (where the data is not recorded directly anywhere else first) Hospital records (from which data will be summarised into the CRF)	
	Objective evidence of graft/repair failure (defined on clinical assessment, imaging or operative assessment	Up to 24 months after randomisation	• Case Report Form.	Hospital records (from which data will be summarised into the CRF)	

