17.1 Overview

Table 1 shows scheduled assessments for the study.

Table 1: Schedule of assessments

Assessments	Screening	Baseline	Day of Surgery	3- & 6-weeks post randomisation	6 months post randomisation	12 months post randomisation	24 months post randomisation
Screening - Identification	*						
Screening - Eligibility	*						
Patient information given	*						
Consent		*					
Eligibility confirmation			*				
Randomisation			*				
Surgeon confidence in the ACL surgery performed (Surgery CRF)			*				
Demographics	*						
Post operative pain (pain NRS) via SMS message, email or post				*			
KOOS (Patient Questionnaire)		*			*	*	*
EuroQol-5D-5L / VAS (Patient questionnaire)		*			*	*	*
EuroQol-5D-5L / VAS Retrospective Baseline - Pre-injury (Patient		*					
questionnaire)							
Emotional functioning (Patient questionnaire)		*			*	*	*
Tegner (Patient questionnaire)					*	*	*
Modified Tegner (Patient questionnaire)		*					
Patient satisfaction (Patient questionnaire)						*	*
Time to return to sport (Patient questionnaire)						*	*
Physio attendance (completed once the pt has been discharged from						*	*
post-op physiotherapy, or at 24 months post-randomisation)							
Resource use /Health economics (Patient questionnaire)					*	*	*
Intervention related complications including re-operation (Patient					*	*	*
questionnaire -> Hospital records check -> Complications CRF)							
+ Intra-operative complications (Surgery CRF)+ Post-operative, pre-discharge complications (InPatient CRF)			*				
Intervention related complications including re-operation (Hospital							*
records check -> Complications CRF)							
Safety data collection			*		*	*	*
Objective evidence of graft/repair failure (defined on clinical assessment, imaging or operative assessment) (Hospital records check) (if required)			*		*	*	*

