17.2.2 Follow-up assessments/subsequent visits

Follow up for study purposes will be by patient self-reported questionnaire completed using a web-based data collection system (REDCap). The option of being able to fill out the follow-up questionnaires in a hard copy and returning via post will also be available. The questionnaires will contain the following outcome measures: KOOS, EQ-5D-5L/VAS, emotional functioning questions taken from KQoL-26, Tegner, and will be sent out at 6-, 12- and 24-months post randomisation to all participants. Patient satisfaction and return to sport outcome measures will be added to the 12- and 24-month questionnaires. The questionnaires will also ask participants if they have returned to see a health care professional or been admitted to hospital in relation to complications with their study knee, and time away from paid employment and education. The central CTU study team will follow up any complications reported by participants with the research team at the participant's local hospital. Further details about the event will be collected and recorded on a complications form.

A final readmission checklist will be undertaken by the Research staff on hospital records at 24 months post randomisation to ensure that all complications data is collected from all participants (i.e. those who had not returned a questionnaire). Data from any readmission events identified will be recorded in a "Complications" CRF. The physiotherapy case report form (PCRF) will be used to record the number of post-operative rehabilitation physiotherapy sessions attended, and the date of discharge from physiotherapy. If a participant attends community-based physiotherapy, the number of sessions attended will be reported via the patient questionnaires.

Patients will also be asked to complete a pain numerical rating scale to report their post operative pain at 3- and 6-weeks post randomisation. A link to complete the score online will be sent by either SMS, email or post. Contact preferences will be recorded in REDCap after consent.

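### The wording of the 24-month hospital-record check limits it to questionnaire non-responders in 17.2.2 and 21.5 but not in Table 1 or 9.3, and does not clearly cover graft/repair failure

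*Protocol*

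**What the plan says.** Five places in the protocol bear on how post-discharge events are found.

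- **Section 21.5** (safety procedure): research staff complete a readmission checklist from hospital records at 24 months so that "all complications data is collected from participants (i.e. those who had not returned a questionnaire").
- **Section 17.2.2** (follow-up): the same sentence, but with *all* before *participants*: "all complications data is collected from all participants (i.e. those who had not returned a questionnaire"). For participants who do reply, the route is triggered by their own report: "The central CTU study team will follow up any complications reported by participants" with the local hospital.
- **Table 1, complications**: there are two rows. One starts from the patient questionnaire at 6, 12 and 24 months. The other, "Intervention related complications including re-operation (Hospital" records check to Complications CRF), is marked at 24 months only and is not limited to any group.
- **Table 1, failure**: a single row, "Objective evidence of graft/repair failure (defined on clinical assessment, imaging or operative assessment) (Hospital records check) (if required"), marked for the day of surgery and for 6, 12 and 24 months. What makes the check required is not stated.
- **Section 9.3**: complications have "Review at the 24-month time point" with no restriction. Graft/repair failure up to 24 months is taken from hospital records.

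Section 23.3.2 analyses graft failure and re-operation by Kaplan-Meier curves and Cox models.

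**The concern.** The abbreviation *i.e.* defines a group; it does not give an example. Section 21.5 therefore limits the check to people who did not return a questionnaire, and 17.2.2 contradicts itself within one sentence. A site working from the safety section could reasonably open only non-responders' records.

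Detection would then follow two rules. A non-responder's record is always searched. A responder's record is searched only if the responder reports something. Which rule applies depends on questionnaire response, which arises after randomisation.

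Graft/repair failure has a further gap. The protocol allows failure to be established by clinical examination or imaging, neither of which needs a readmission. A readmission checklist need not find such cases, and the one row that names failure is conditional on an undefined trigger. This gap remains even if the checklist is completed for everyone.

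At stake are the completeness of the complications data and the event counts for two secondary time-to-event outcomes.

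**Working it through.** There is no protocol figure to reproduce, because the point rests on wording.

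**Step 1: who is checked at 24 months?**
- 21.5: participants, defined as non-responders.
- 17.2.2: all participants, then defined as non-responders.
- Table 1, second complications row: no restriction, and separate from the questionnaire-triggered row.
- 9.3: no restriction.

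The four statements cannot all be followed. The existence of two Table 1 rows suggests that a check not triggered by self-report was planned for everyone.

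**Step 2: which questionnaire?** Questionnaires go out at 6, 12 and 24 months. The gloss does not say whether missing one, missing the last or missing all of them puts a participant in the group, so even the literal reading cannot be applied uniquely.

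**Step 3: is failure covered?** 9.3 defines failure by clinical, imaging or operative evidence. The checklist in 17.2.2 and 21.5 records readmission events. The Table 1 failure row is conditional. No passage commits to an untriggered 24-month search for failures found without readmission.

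**Step 4: can the loss be sized?** Under the literal reading, the share of all events missed is at most p × u, where p is the share of events occurring in responders and u is the fraction of those not reported. The protocol gives neither. As an illustration only, take p = 0.85, treating the 15% missing-data allowance in 23.2 as the non-responder share and assuming equal event risk in the two groups. Take u from 5% to 30%, an assumption without a source.
- Share missed: 0.85 × 0.05 = 0.04 to 0.85 × 0.30 = 0.26.
- With an assumed 24-month event rate of 5% to 15% among 214 randomised: 214 × 0.85 × 0.05 × 0.05 = 0.5 events to 214 × 0.85 × 0.15 × 0.30 = 8.2 events, out of about 11 to 32.

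The range is too wide to serve as an estimate. These figures are also upper bounds for the chosen inputs, because related SAE reports and other site records would recover some events. The 15% is an allowance for missing data by 24 months, not the share who missed any questionnaire.

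**Step 5: what would checking everyone cost?** The largest possible load is 214 / 20 sites = 10.7 records per site, once. If non-responders' records were already to be checked, the extra is 214 × 0.85 / 20 = 9.1 per site at 15% non-response. At 22%, the missing-data level that 23.2 quotes from the earlier ACL trial at 18 months, it is 214 × 0.78 / 20 = 8.3.

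**The case against.** The strongest reply is that this is a drafting slip. Section 17.2.2 says *all*, Table 1 has an unrestricted 24-month records row, 9.3 has an unrestricted review, and the main clause in 21.5 describing the check carries no limit. The author probably wrote *i.e.* for *including*. This stands as the likeliest account of intent, so the protocol should not be read as a settled decision to leave responders' records unopened. It does not remove the conflict, because 21.5 is the section that tells sites how to collect safety events.

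A second reply is that sites must report related SAEs within 24 hours of becoming aware of them, whether or not a questionnaire came back, and that hospitalisation makes an event serious. This also stands in part, so the 24-month check is not the only untriggered route. But it reaches only events that are serious, judged related and known to the site. A failure seen in clinic or on imaging may not be serious. Graft failure and revision operation are on the expected list in 21.3. Section 21.6 refers to 21.4 for events that need no reporting, and 21.4 deals with expected serious events in terms of REC reporting, so it is unclear how fully this route captures them.

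Third, responders are asked up to three times about health-care contact or admission for the study knee, which should keep under-reporting down. That is fair, and it is one reason the loss cannot be sized.

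A reader might go further and infer that the Cox hazard ratio is biased. The documents do not support this. It would need response or self-reporting to differ by arm, and section 18.1 plans to blind participants and follow-up staff. A similar shortfall in both arms mainly costs events. On the conditional failure check, it is reasonable for it to be conditional at the earlier time points; the difficulty is at 24 months.

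**Conclusion.** The point holds as a wording conflict with a practical consequence. Sections 17.2.2 and 21.5 limit the 24-month check in words that Table 1 and 9.3 do not share, and no passage clearly commits to an untriggered 24-month search for graft/repair failure. If 21.5 is followed literally, events that a responder does not report, and that do not reach the site as a related SAE, could be missed, and detection would depend on questionnaire response.

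The effect is confined to complications and to the secondary outcomes of re-operation and graft/repair failure; KOOS-4 at 24 months is untouched. The number of events at risk cannot be derived from the protocol, and no difference between arms is shown. The conclusion rests on the literal reading being the one a site might follow, not on that reading being the intended one. It is worth correcting because the correction is cheap and must precede the 24-month checks to be useful.

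**What to change.** Make 17.2.2, 21.5 and Table 1 say the same thing:

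- The 24-month hospital-record check is made for every randomised participant who has not withdrawn access to records (17.6 provides for this withdrawal), whether or not any questionnaire was returned. Remove the *i.e.* gloss.
- The check covers re-operation and graft/repair failure, on clinical, imaging or operative evidence, as well as readmissions.
- In Table 1, remove *if required* from the failure check at 24 months. If it stays for the earlier time points, state what triggers it.

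If everyone was already meant, the cost is wording only. If not, it is a modest number of extra one-off checks: about 8 to 9 per site under the non-response levels shown above, and no more than about 11 per site in any case.
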